Table 4-3:	Tipping point analysis: Delta parameters for each ACR component	45
Table 4-4:	Sequential testing procedure of primary/ secondary efficacy endpoints (fixed sequence testing procedure) (All efficacy endpoints at Week 16)	50
Table 8-1:	Swelling and tenderness grading	61
Table 8-2:	Aid or device associated with HAQ-DI category	63
Table 8-3:	Five-point IGA	73
Table 8-4:	Normative values for LDI	82
Table 10-1:	Type of extended MACE events	107
Table 10-2:	Laboratory measurements	111
Table 10-3:	Definitions of markedly abnormal biochemistry values	112
Table 10-4:	Definitions of markedly abnormal hematology values	113
Table 10-5:	Definitions of markedly abnormal liver enzyme elevation values	114
Table 10-6:	Definitions of markedly abnormal blood pressure values	116

LIST OF FIGURES

Figure 2-1:	Study schematic design	19
-------------	------------------------------	----

LIST OF ABBREVIATIONS

ACR	American College of Rheumatology
ACR20,50,70	American College of Rheumatology 20, 50, 70% response criteria
ADAb	anti-drug antibody
ADR	adverse drug reaction
AE	adverse event
ANCOVA	analysis of covariance
ATC	anatomical therapeutic chemical classification
BASDAI	Bath Ankylosing Spondylitis Disease Activity Index
BKZ	bimekizumab
BLQ	below the limit of quantification
BMI	body mass index
BP	blood pressure
BSA	body surface area
CASPAR	Classification Criteria for Psoriatic Arthritis
CCP	cyclic citrullinated peptide
cDMARD	conventional disease modifying antirheumatic drug
CI	confidence Interval
COVID-19	Coronavirus Disease 2019
CRF	case report form
CRP	C-reactive protein
CV	coefficient of variation
DAPSA	disease activity index for psoriatic arthritis
DAS28[CRP]	disease activity score-28 based on C-reactive protein

DILI	drug-induced liver injury
DMC	data monitoring committee
DMARDs	disease modifying antirheumatic drugs
ECG	electrocardiogram
eC-SSRS	electronic Columbia-Suicide Severity Rating Scale
EQ-5D-3L	Euro-Quality of Life 5-Dimensions 3 Level version
ET	early termination
EAER	exposure adjusted event rate
EAIR	exposure adjusted incidence rate
FACIT	Functional Assessment of Chronic Illness Therapy
FAS	full analysis Set
FDA	Food and Drug Administration
HAQ-DI	Health Assessment Questionnaire - Disability Index
HLA-B27	human leukocyte antigen B27
HLT	high level term
hs-CRP	high sensitivity C-reactive protein
ICH	International Council for Harmonisation of Technical Requirements for Pharmaceuticals for Human Use
IE	intercurrent event
IGA	Investigator's Global Assessment
IMP	investigational medicinal product
IPD	important protocol deviation
IWRS	interactive web response system
KM	Kaplan-Meier

LCL	lower confidence limit
LDI	Leeds Dactylitis Index
LEI	Leeds Enthesitis Index
LLOQ	lower limit of quantification
LN	natural logarithm
LSM	least square means
MACE	major adverse cardiac events
MAR	missing at random
MCMC	Markov-Chain Monte Carlo
MCS	Mental Component Summary
MDA	minimal disease activity
MedDRA	medical dictionary for regulatory activities
MI	multiple imputation
mNAPSI	modified Nail Psoriasis Severity Index
MTX	methotrexate
NAb	neutralizing anti-bimekizumab antibodies
NRI	nonresponder imputation
NRS	numeric rating scale
NSAID	nonsteroidal anti-inflammatory drug
OC	observed cases
OLE	open label extension
OR	odds ratio
PASDAS	psoriatic arthritis disease activity score
PASI	psoriasis area and severity index

PASI75, PASI90, PASI100	psoriasis area and severity index 75%, 90%, 100%
PCS	Physical Component Summary
PGA-Arthritis	Patient's Global Assessment of arthritis
PGA-PsA	Patient's Global Assessment of Psoriatic Arthritis
PhGA-Arthritis	Physician's Global Assessment of arthritis
PhGA-PsA	Physician's Global Assessment of Psoriatic Arthritis
PHQ-9	Patient Health Questionnaire-9
PK-PPS	pharmacokinetics per-protocol set
PPS	per-protocol set
PsA	psoriatic arthritis
PsAID-12	Psoriatic Arthritis Impact of Disease-12
PsARC	psoriatic arthritis response criteria
PsAQoL	Psoriatic Arthritis Quality of Life
PSO	psoriasis
PT	preferred term
PtAAP	Patient's Assessment of Arthritis Pain
Q4W	every 4 weeks
RS	randomized set
SAE	serious adverse event
SAP	statistical analysis plan
SC	subcutaneously
SD	standard deviation
SF-36	Short-Form 36-item Health Survey
SFU	safety follow-up

SOC	system organ class
SPARCC	Spondyloarthritis Research Consortium of Canada
SJC	swollen joint count
SMQ	standardized MedDRA query
SS	safety set
TB	tuberculosis
TEAE	treatment emergent adverse event
TESAE	treatment emergent serious adverse event
TFLs	tables, figures, and listings
TJC	tender joint count
TNF	tumor necrosis factor
TNF α	tumor necrosis factor alpha
TNF α -IR	TNF α -inadequate responders
UCL	upper confidence limit
ULN	upper limit of normal
VAS	visual analog scale
WHO-DD	World Health Organization Drug Dictionary
VLDA	very low disease activity
WPAI-SHP	Work Productivity and Activity Impairment questionnaire - Specific Health Problem

1 INTRODUCTION

This statistical analysis plan (SAP) provides the necessary information to perform the final statistical analysis as well as the interim analysis for study PA0011. It also defines the summary tables, figures, and listings (TFLs) to be generated for the final clinical study report.

The SAP is based on Protocol Amendment 2 (1 APR 2021). All references to study protocol hereafter refer to this version of the protocol, and, unless otherwise specified, the study will be analyzed as described in this version of the protocol. If a future protocol amendment necessitates a substantial change to the statistical analysis of the study data, or if analysis definitions must be modified or updated, this SAP will be amended accordingly.

The content of this SAP is compatible with the International Council for Harmonisation of Technical Requirements for Pharmaceuticals for Human Use (ICH)/Food and Drug Administration (FDA) E9 Guidance documents (ICH E9, 1998).

2 PROTOCOL SUMMARY

2.1 Study objectives

2.1.1 Primary objective

The primary objective is to demonstrate the clinical efficacy of bimekizumab (BKZ) administered subcutaneously (sc) every 4 weeks (Q4W) for 16 weeks compared with placebo in the treatment of prior tumor necrosis factor alpha-inadequate responders (TNF α -IR) subjects with active psoriatic arthritis (PsA), as assessed by the American College of Rheumatology 50% (ACR50) response.

2.1.2 Secondary objectives

The secondary objectives are as follows:

- To assess the efficacy of bimekizumab compared with placebo
- To assess the safety and tolerability of bimekizumab
- To assess the impact of bimekizumab on patient-reported quality of life
- To assess the impact of bimekizumab on skin psoriasis (PSO) in the subgroup of affected subjects at Baseline.
- To assess the impact of bimekizumab on functional improvement

2.1.3 Other objectives

Other objectives are as follows:

- To assess the immunogenicity of bimekizumab
- To assess the impact of bimekizumab on extra-articular disease manifestations (dactylitis, enthesitis)
- To assess nail PSO in the subgroup of affected subjects at Baseline
- To explore the exposure-response relationship of bimekizumab
- To assess the impact of bimekizumab treatment on axial disease

- To assess the effect of bimekizumab on gene and protein expression, and explore the relationship between genomic, genetic, and proteomic biomarkers and disease biology, drug treatment and inflammatory and immune responses (from consenting subjects who agree to participate in the biomarkers sub-study)
- To assess the impact of bimekizumab on social life and work productivity

2.2 Study variables

2.2.1 Efficacy variables

2.2.1.1 Primary efficacy variable

The primary efficacy variable is the ACR50 response at Week 16.

2.2.2 Secondary variables

2.2.2.1 Secondary efficacy variables

The secondary efficacy variables are as follows:

- Change from Baseline in Health Assessment Questionnaire - Disability Index (HAQ-DI) at Week 16
- Reduction of 90% from Baseline in Psoriasis Area and Severity Index (PASI90 response) at Week 4 and Week 16 in the subgroup of subjects with PSO involving at least 3% body surface area (BSA) at Baseline
- Change from Baseline in the Short-Form 36-item Health Survey (SF-36) Physical Component Summary (PCS) score at Week 16
- Minimal Disease Activity (MDA) response at Week 16
- ACR20 response at Week 16
- ACR70 response at Week 16
- Proportion of subjects with an Investigator Global Assessment (IGA) score of 0 (clear) or 1 (almost clear) AND at least a 2-grade reduction from Baseline at Week 4 and Week 16 in the subset of subjects with psoriatic skin lesions at Baseline
- Change from Baseline in the Patient's Assessment of Arthritis Pain (PtAAP) at Week 16
- Change from Baseline in Psoriatic Arthritis Impact of Disease-12 (PsAID-12) total score at Week 16

2.2.2.2 Secondary safety variables

Secondary safety variables to be assessed are as follows:

- Incidence of treatment-emergent adverse events (TEAEs)
- Incidence of treatment-emergent serious adverse events (TESAEs)
- TEAEs leading to withdrawal from Investigational Medicinal Product (IMP)

2.2.3 Other variables

2.2.3.1 Other efficacy variables

The following other efficacy variables will be assessed (all time points not specified in [Section 2.2.1.1](#) or [Section 2.2.2.1](#) are exploratory):

- Time to ACR20, ACR50, and ACR70 response from Baseline (Day 1)
- ACR20, ACR50 and ACR70 response
- PASI75, PASI90 and PASI100 response in the subgroup of subjects with PSO involving at least 3% BSA at Baseline
- Composite endpoint composed of ACR50 and PASI90 response in subjects with PSO involving at least 3% BSA at Baseline
- Composite endpoint composed of ACR50 and PASI100 response in subjects with PSO involving at least 3% BSA at Baseline
- Proportion of Psoriatic Arthritis Response Criteria (PsARC) responders
- Psoriatic Arthritis Disease Activity Score (PASDAS) categories
- Change from Baseline in the PASDAS
- MDA response
- Very Low Disease Activity (VLDA) response
- Proportion of subjects with an IGA score of 0 (clear) or 1 (almost clear) AND at least a 2-grade reduction from Baseline in the subset of subjects with psoriatic skin lesions at Baseline
- Disease Activity Index for Psoriatic Arthritis (DAPSA) score categories,
- Change from Baseline in DAPSA score
- Change from Baseline in the Disease Activity Score-28 based on C-reactive protein (DAS28 [CRP])
- Change from Baseline in all individual ACR core components:
 - Swollen Joint Count (SJC)
 - Tender Joint Count (TJC)
 - HAQ-DI
 - PtAAP
 - Physician's Global Assessment for Psoriatic Arthritis (PhGA-PsA)
 - Patient's Global Assessment for Psoriatic Arthritis (PGA-PsA)
 - High sensitivity C-reactive protein (hs-CRP)
- Enthesitis-free state based on the Leeds Enthesitis Index (LEI) in the subgroup of subjects with enthesitis at Baseline (ie, LEI>0 at Baseline)

- Change from Baseline in the LEI in the subgroup of subjects with enthesitis at Baseline (ie, LEI>0 at Baseline)
- Enthesitis-free state based on the Spondyloarthritis Research Consortium of Canada (SPARCC) index in the subgroup of subjects with enthesitis at Baseline (ie, SPARCC>0 at Baseline)
- Change from Baseline in SPARCC index in the subgroup of subjects with enthesitis at Baseline (ie, SPARCC>0 at Baseline)
- Dactylitis-free state based on the Leeds Dactylitis Index (LDI) in the subgroup of subjects with dactylitis at Baseline (LDI>0)
- Change from Baseline in the LDI in the subgroup of subjects with dactylitis at Baseline (LDI>0)
- Proportion of subjects with a decrease of HAQ-DI from Baseline of at least 0.35 in the subgroup of subjects with Baseline HAQ-DI \geq 0.35
- Change from Baseline in the Bath Ankylosing Spondylitis Disease Activity Index (BASDAI) in the subgroup of subjects with axial involvement defined by a score of \geq 4 at Baseline
- Change from Baseline in the modified Nail Psoriasis Severity Index (mNAPSI) score in the subgroup of subjects with psoriatic nail disease at Baseline (mNAPSI score>0)
- Change from Baseline in PsAID-12 total score
- Change from Baseline in the individual domain scores of PsAID-12
- Proportion of subjects achieving PsAID-12 total score \leq 4
- Proportion of PsAID-12 responders (decrease from Baseline in PsAID-12 total score \geq 3) in subjects with PsAID-12 total score \geq 3 at Baseline
- Change from Baseline in the Psoriatic Arthritis Quality of Life (PsAQoL) total score
- Change from Baseline in the SF-36 PCS and SF-36 Mental Component Summary (MCS), as well as the 8 domain scores of the SF-36 (Physical Functioning, Role Physical, Bodily Pain, General Health, Vitality, Social Functioning, Role Emotional, and Mental Health)
- Change from Baseline in Functional Assessment of Chronic Illness Therapy (FACIT)-Fatigue subscale score
- Proportion of FACIT-Fatigue subscale responders (subjects with a minimum clinically-important difference for FACIT-Fatigue subscale score, defined as an increase of \geq 4) in subjects with FACIT-Fatigue subscale score \leq 48 at Baseline
- Change from Baseline in Work Productivity and Activity Impairment Questionnaire-Specific Health Problem (WPAI-SHP) v2.0 adapted to PsA scores
- Responses to the EuroQol-5D-3-Level (EQ-5D-3L) dimensions
- Change from Baseline in EQ-5D-3L Visual Analog Scale (VAS) scores
- Change from Baseline in Physician's Global Assessment of Arthritis (PhGA-Arthritis)

- Change from Baseline in Patient's Global Assessment of Arthritis (PGA-Arthritis)

2.2.3.2 Other safety variables

Other safety variables to be assessed are:

- Change from Baseline in vital signs (blood pressure [BP], temperature, and pulse rate)
- Standard 12-lead electrocardiogram (ECG) results
- Change from Baseline in clinical laboratory values (hematology, biochemistry and urinalysis)
- Change from Baseline in Patient Health Questionnaire-9 (PHQ-9)

Physical examination findings considered clinically significant changes since the physical examination at the Screening Visit will be recorded as AEs.

2.2.3.3 Pharmacokinetic variable

The pharmacokinetic (PK) variable is the plasma concentration of BKZ. Blood samples for these measurements will be obtained at all visits except Screening.

2.2.3.4 Pharmacogenomic variables

Additional blood samples will be collected from subjects who consent to participate in the sub study at specific time points and stored at -80°C for up to 20 years.

Genomic, genetic, epigenetic, proteins, and metabolite biomarkers may be measured to evaluate the relationship with response to treatment with BKZ, PsA disease biology, and inflammatory and immune response processes. The nature and format of these tentative sub study analyses will be determined when the results of the main study are made available.

The candidate exploratory variables are the blood or blood derivative (eg, serum) concentrations of cytokines and chemokines of relevance to IL-17A/F signaling pathway and PsA biology. Additional variables may include but will not be limited to serum complement concentrations.

2.2.3.5 Immunological variables

The immunological variables allow evaluation of immunogenicity. The immunological variables are:

- The anti- BKZ antibody status
- The treatment-emergent antibody status derived from antidrug antibody (ADAb) assays
- The neutralizing antidrug antibody (NAb) status

These 3 variables will be assessed at all visits except Screening.

2.3 Study design and conduct

2.3.1 Study description

PA0011 is a Phase 3, multicenter, randomized, double-blind, placebo-controlled study. To be eligible to participate in this study, subjects must be adults with a diagnosis of PsA based on the Classification Criteria for Psoriatic Arthritis (CASPAR) criteria and have disease with TJC ≥ 3 and SJC ≥ 3 , as well as an inadequate response (lack of efficacy after at least 3 months of therapy

at an approved dose) or intolerance to treatment with 1 or 2 TNF α inhibitors for either PsA or PSO. Study entrance criteria are described in the protocol.

The study consists of the following periods (see [Figure 7–1](#) for a schematic diagram).

- a Screening Period (≥ 14 days to ≤ 35 days),
- a 16-week placebo-controlled Double-Blind Treatment Period,
- and a Safety Follow-Up (SFU) Period, 20 weeks after the final dose of IMP (for subjects who complete the study and do not enter the open-label extension (OLE) study or for subjects who discontinue early, including those withdrawn from IMP).

The maximum study duration per subject will be up to 37 weeks. The end of the study is defined as the date of the last visit of the last subject in the study.

[figure not shown]
Approximately 390 subjects will be randomized in a 2:1 ratio, stratified by region (North America, Western Europe, Eastern Europe, and Asia) and prior TNF α inhibitor exposure (inadequate response to 1 prior TNF α inhibitor, inadequate response to 2 prior TNF α inhibitors, or intolerance to TNF α inhibitor) to receive one of the two following blinded treatment groups:

- Bimekizumab 160mg sc Q4W,
- Placebo

Subjects discontinuing IMP during the Double-Blind Treatment Period will be encouraged to return for all scheduled visits through Week 16 and the SFU Visit, as applicable.

At the completion of the Double-Blind Treatment Period, subjects completing the study (ie, performing all visits up to Week 16 and not having permanently discontinued IMP) and who did not meet any of the withdrawal criteria will be given the opportunity to enter an OLE study at Week 16.

Figure 7–1: Study schematic diagram

ACR50=American College of Rheumatology 50% response criteria; Q4W=every 4 weeks; SFU=Safety Follow-Up; sc=subcutaneous; W=week

Refer to the clinical study protocol for more detailed information on the study assessments and schedule of procedures.

2.3.2 Study periods

The following study periods are defined for the classification by study period:

Screening Period (≥14 days to ≤35 days)

Starts at time of the informed consent date (Screening Visit - Visit 1) and ends the day before the first dose administration of IMP (Baseline Visit – Visit 2) (ie, generally the day before Visit 2 date). This period should last between 14 to 35 days and will involve obtaining laboratory data and verifying that the doses of nonsteroidal anti-inflammatory drugs (NSAIDs) or permitted DMARDs, if used to treat PSA, are stable. The Screening Period will also enable washout of any medications not permitted for use during the study.

Double-Blind Treatment Period (16 weeks)

Starts on the day of first dose administration of study drug (Visit 2). This period should last 16 weeks maximum. During the Double-Blind Treatment Period, subjects will be randomized 2:1 (stratified by region and prior TNF α inhibitor exposure [inadequate response to 1 or 2 prior TNF α inhibitors, or intolerance to TNF α inhibitors]) to receive 1 of 2 blinded treatment regimens:

- Bimekizumab 160mg sc Q4W,
- Placebo

Visit windows of ± 3 days are allowed from the first dose at all visits through Week 16. The visit window is relative to the Day 1 (Baseline) Visit.

Bimekizumab and placebo will be administered sc by unblinded study personnel at the clinical site.

The time between IMP doses should be ≥ 21 days and ≤ 35 days during the Double-Blind Treatment Period.

Subjects discontinuing IMP during the Double-Blind Treatment Period will return for all scheduled visits through Week 16 and the SFU Visit (20 weeks after the final dose of IMP) as applicable. Subjects withdrawing from the study will have an Early Termination (ET) Visit and a SFU Visit 20 weeks after the final dose of IMP, as applicable.

The end of the 16-week Double-Blind Treatment Period will be either the date of Week 16 visit (Visit 6) for subjects completing the treatment period, or the date of the early termination (ET) visit for subjects who discontinued during the Treatment Period.

If a subject does not have a Visit 6 or ET visit, then either the date of the last scheduled or unscheduled visit during the Treatment Period or the date of last known dose of study drug during the Treatment Period, whichever is later, will define the end date of the Treatment Period.

Safety Follow-Up

The SFU Period will be defined for all subjects who complete the study and do not enter the OLE study, or for subjects who discontinue early including those withdrawn from IMP. This period should last 20 weeks from the final dose.

- For subjects who complete the study and do not enter the OLE study, the SFU Period starts the day after Visit 6 date and ends on the day of the SFU Visit.
- For subjects who discontinue early, the SFU Period starts the day after the ET date and ends on the day of the SFU Visit

A subject will be considered to have completed a study period if they complete the last scheduled study visit for that period. Note that subjects who previously discontinued IMP and are continuing for all scheduled visits through Week 16 will also be considered as completed the Double-Blind Treatment Period.

2.4 Determination of sample size

Approximately 390 subjects will be randomly assigned in a 2:1 ratio to the following treatment groups: BKZ 160mg sc Q4W (260 subjects) and placebo (130 subjects).

The primary efficacy analysis is based on the primary comparison of BKZ versus placebo for ACR50 response at Week 16.

All sample size and power calculations were done at a significance level of 0.05.

All sample size and power calculations were performed using the software nQuery Advisor® 7.0.

2.4.1 Power calculation for primary endpoint

The sample size assumptions for BKZ vs placebo are based on the ACR50 response data in the subgroup of TNF α -IR patients from the Phase 2b BKZ study in a mixed prior TNF α therapy

population of subjects with moderate-to-severe PsA (PA0008). Sample size calculations for a TNF α -IR population are also based on ACR50 responses at Week 16 in the SPIRIT-P2 study.

Observed ACR50 at Week 12 results in the PA0008 TNF α -IR populations were in a small number of subjects; BKZ 160mg (n=7), 320mg (n=8), and 320mg (initial dose) plus 160mg (n=8) and ranged from 14.3% to 37.5%.

The ixekizumab Phase 3 study SPIRIT-P2 is conducted on a similar patient population to that in this study and showed a 35% (n=122) ACR50 response at Week 16. Therefore, taking into account the range of ACR50 responses at Week 12 in PA0008, the estimated ACR50 response at Week 16 in the BKZ 160mg sc Q4W group is conservatively assumed to be 26%.

For placebo, a similar approach as above is used. In the PA0008 TNF α -IR population, an ACR50 response of 11.1% (n=9) was observed at Week 12. The observed placebo ACR50 response at Week 16 was less than 10% in the SPIRIT-P2 study (n=118). Therefore, the estimated ACR50 response at Week 16 in the placebo group is assumed to be 10%.

The sample size for showing statistical superiority of BKZ vs placebo was calculated using a 2-sided 2-sample Chi-square test with continuity correction (Fleiss et al, 1980). Assuming 260 subjects in the BKZ group and 130 subjects in the placebo group, the test for detecting statistical superiority of BKZ 160mg vs placebo based on ACR50 response at Week 16 has 96% power to detect a true treatment difference of 16% (odds ratio (OR) of 3.16).

2.4.2 Power calculation for secondary endpoints

The assumptions for power calculations of the secondary endpoints included in the hierarchy and for which supporting data are available, in the TNF α -IR population are based on the results of PA0008 and the SPIRIT-P2 studies. All power calculations for binary endpoints were performed using a 2-sided 2-sample Chi-square test with continuity correction (Fleiss et al, 1980). All power calculations for continuous endpoints were performed using a 2-sided 2-group Satterthwaite t-test (Moser et al, 1989).

For the change from Baseline in HAQ-DI at Week 16, based on data from the TNF α -IR population in SPIRIT-P2 Week 12 as well as Week 12 and Week 16 data from the PA0008 and PsA001 studies respectively, estimates of the SD in the active treatment and placebo groups are 0.71. A two-group Satterthwaite t-test with a 0.050 2-sided significance level will have 85% power to detect a difference of 0.23 in the mean change from Baseline in HAQ-DI at Week 16 between BKZ treatment and placebo assuming a sample size of 390 subjects randomized 2:1.

For PASI90 response at Week 16, a PASI90 response at Week 12 of 38% (N=122), from the SPIRIT-P2 study is assumed. The PASI90 response at Week 12 in the BKZ 160mg group is 50.0% (n=8) in the subgroup analysis of the TNF α -IR patients. Placebo PASI90 response at Week 16 is based on SPIRIT-P2 data (6.0% at Week 12). However, for this endpoint the placebo response is rounded to 10%. With those assumptions, the endpoint has 99% power to detect a treatment difference of 28% (OR of 5.52) at an assumed 50% of subjects with BSA \geq 3% of the planned sample size.

For the change from Baseline in PCS score of SF-36 at Week 16, based on data from the TNF α -IR population in SPIRIT-P2 where estimates of the SD in the active treatment and placebo groups at Week 12 are ixekizumab Q4W (SD=11.95) and placebo (SD=12.15). A 2-group Satterthwaite t-test with a 0.050 2-sided significance level will have 89% power to detect a

difference in means of 4.4 change from Baseline in SF-36 PCS score at Week 16 between the bimekizumab and placebo treatment groups with a sample size of 390 subjects randomized 2:1.

For MDA at Week 16, it is assumed that 5% of the placebo subjects achieve MDA at Week 16 (SPIRIT-P2 Week 12). Given the planned sample size and using a 2-sided 2-sample Chi-square test with continuity correction this study has 92% power to detect an absolute difference in MDA response at Week 16 of 12% (OR of 3.892) with a total sample size of 390 subjects.

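### The 89% power stated for SF-36 PCS (H4) does not follow from its own inputs, which give 92%

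*SAP*

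**What the plan says.** Section 2.4 plans 390 subjects, 260 on bimekizumab and 130 on placebo, and adds: "All sample size and power calculations were done at a significance level of 0.05". For continuous endpoints, section 2.4.2 fixes the method: "All power calculations for continuous endpoints were performed using a 2-sided 2-group Satterthwaite t-test".

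For SF-36 PCS, section 2.4.2 takes the SDs from Week 12 of an earlier trial of another drug: "ixekizumab Q4W (SD=11.95) and placebo (SD=12.15". The power claim reads "2-sided significance level will have 89% power to detect a", with alpha set at 0.050. The effect on which that claim rests is given as a "difference in means of 4.4 change from Baseline in SF-36 PCS score at Week 16". The numbers are those of the whole trial: "treatment groups with a sample size of 390 subjects randomized 2:1". No dropout allowance or reduced evaluable number is given for this endpoint, and none appears elsewhere in section 2.4.

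The SF-36 PCS change is H4 in the fixed sequence of section 4.5, directly before MDA (H5).

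**The concern.** The SAP prints every quantity needed to compute this power, and the result is not the power that it prints. At least one of five items must therefore be misreported: the power, the difference, one of the two SDs, or the number of subjects.

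The stake is the planning record for H4. A reader who wants to judge whether the assumed effect and variability were realistic cannot tell which assumptions were used. Because MDA can be tested only if H4 is rejected, the PCS power also bears on the planned chance of reaching H5. The SAP makes no joint or sequential power claim, however, so no other stated figure depends on the 89%.

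**Working it through.** **Inputs (SAP sections 2.4 and 2.4.2)**

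- Arms: n₁ = 260 (bimekizumab), n₂ = 130 (placebo)
- Difference: 4.4
- SDs: 11.95 (active), 12.15 (placebo)
- Two-sided α = 0.05, Satterthwaite t-test

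**Step 1: calibrate on the other continuous endpoint.** HAQ-DI uses the same test and the same arms, with difference 0.23 and SD 0.71.

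- SE = √(0.71²/260 + 0.71²/130) = 0.0763
- Noncentrality = 0.23/0.0763 = 3.02, df = 258
- Power from the noncentral t distribution = 85.2%. The SAP states 85%, so the figure reproduces.

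**Step 2: apply the same routine to SF-36 PCS.**

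- SE = √(s₁²/n₁ + s₂²/n₂) = √(11.95²/260 + 12.15²/130) = √(0.549 + 1.136) = 1.298
- Satterthwaite df = (0.549 + 1.136)² / (0.549²/259 + 1.136²/129) = 254
- Noncentrality = 4.4/1.298 = 3.39, critical t = 1.969
- Power = 92.2%. The SAP states 89%, so the figure does not reproduce.

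A normal approximation gives 92.4%, and a simulation of the unequal-variance t-test with 200,000 replicates gives 92.2%.

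**Step 3: check the remaining power statements.** The binary endpoints use the continuity-corrected chi-square test named in the SAP.

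| Endpoint | Inputs | Recomputed | Stated |
|---|---|---|---|
| ACR50 | 26% vs 10%, 260/130 | 96.6% | 96% |
| HAQ-DI | 0.23, SD 0.71, 260/130 | 85.2% | 85% |
| PASI90 | 38% vs 10%, 130/65 | 99.1% | 99% |
| SF-36 PCS | 4.4, SDs 11.95/12.15, 260/130 | **92.2%** | **89%** |
| MDA | 17% vs 5%, 260/130 | 92.5% | 92% |

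Four of the five agree to within a point.

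**Step 4: try variants of the PCS calculation at 390 subjects.**

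| Variant | Power |
|---|---|
| Common SD 11.95 / 12.05 / 12.15 (normal approximation) | 92.9% / 92.5% / 92.1% |
| SDs swapped between arms | 92.5% |
| Difference 4.35 (lowest value that rounds to 4.4) | 91.6% |
| One-sided 0.05 | 95.9% |
| Two-sided 0.025 | 87.1% |
| 1:1 allocation | 94.9% |
| Rank test at 0.955 efficiency | 91.0% |

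None gives 89%.

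**Step 5: find what would give 89%, changing one input at a time.**

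- Difference of about 4.15: 89.0%
- Common SD of about 12.8: 89.0%
- About 348 evaluable subjects (232/116): 89.0%; 10% loss, that is 351 subjects (234/117): 89.3%

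The SAP states none of these.

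**The case against.** The best candidate explanation is an unstated allowance for about 10% loss, which would bring PCS to 89.3%. It does not rescue the statement. The PCS sentence itself names 390 subjects. Nor can the allowance have been general: at 234/117, HAQ-DI would fall to 81.3% (stated 85%), ACR50 to 94.5% (96%), MDA to 89.0% (92%), and PASI90 at half that sample to 98.2% (99%). If it was applied to PCS alone, the number of subjects is the misreported item.

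Rounding does not help either. ACR50 recomputes to 96.6% against a stated 96%, so powers may have been truncated, but that is worth less than one point against a gap of 3.2.

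The objection on weight is stronger, and most of it stands. The printed figure understates the power that its inputs deliver. The trial size is presented on the basis of ACR50, with 390 taken as given for the secondary endpoints. Correcting the figure changes no test, alpha level, testing order or estimand. The planned analysis is a baseline-adjusted ANCOVA after reference-based imputation (section 4.2.2.3), so the t-test power is an approximation in any case. The SDs are borrowed from Week 12 of another drug's trial, which brings uncertainty of its own.

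It is also fair that the SAP does not show 89% to be the wrong item rather than one of the inputs. The remedy must leave that open.

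**Conclusion.** The point holds. With the stated test, alpha, difference, SDs and arm sizes, the power for SF-36 PCS is 92.2%, not 89%: a gap of 3.2 percentage points that neither rounding nor any of the variants tried explains. The result rests only on figures printed in sections 2.4 and 2.4.2, and on reading 390 at 2:1 as 260 and 130, which section 2.4 states.

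The defect is confined to this one statement; the other four powers reproduce. If the inputs are right, the error is conservative. If 89% is right, the assumed difference was smaller, the SD larger or the evaluable number lower than printed, and the SAP misreports the planning assumption for H4. Sample size and control of the type I error are not affected in either case.

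**What to change.** Check the original power output for SF-36 PCS and reconcile the sentence in section 2.4.2 with it:

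- If the difference of 4.4, the SDs of 11.95 and 12.15 and the 390 subjects are confirmed, restate the power as 92%.
- If 89% came from another difference, SD or evaluable number, print that input with its reason, and keep 89%.

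The cost is one figure, or one input with a short reason, in the SAP. The sample size, the hierarchy and the analysis stay as they are.
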